**REVISION HISTORY**

Revision #	Version Date	Summary of Changes	Consent Change?
		Crossover to new template	n/a

PROTOCOL TITLE:

VERSION DATE:

#### **ABBREVIATIONS/DEFINITIONS**

- tDCS – Transcranial Direct Current Stimulation
- EEG – Electroencephalograph
- ERP – Event Related Potential
- SSP – Stimulus Specific Plasticity
- AEP – Auditory Evoked Potential

PROTOCOL TITLE:

VERSION DATE:

## 1.0 Objectives

- 1.1 Purpose: *Experience dependent plasticity is a fundamental property of the brain. It allows neural systems to adapt in response to environmental input and subserves the vital functions of learning and memory. Deficits in plasticity are also thought to play a causal role in the pathophysiology of several psychiatric disorders, specifically schizophrenia (SZ). Treatments that can probe or even enhance plasticity have potential to be of great clinical and research value. Non-invasive neuromodulation via transcranial direct current stimulation (tDCS) is a promising method for modulating neural plasticity. tDCS delivers low-intensity direct current to cortical areas, thereby facilitating or inhibiting neural activity in a polarity specific manner. Due to its low cost and safety, tDCS has been employed in a wide variety of studies, but much remains unknown regarding its mechanism of action in humans. Experiments carried out in animal and tissue models indicate that tDCS modulates synaptic plasticity mechanisms of long term potentiation and depression (LTP/D), however, these findings have never been translated to human subjects, limiting the practical utility of the research. Recently developed electroencephalographic (EEG) based measures now allow the interrogation of synaptic plasticity non-invasively in humans, making it possible to explore the effects of tDCS on human brain plasticity.*

### **Specific Aims:**

- 1. Evaluate the effects of Anodal tDCS vs. Sham in enhancing the induction of plasticity in the auditory cortex in healthy participants.**

**Hypothesis: Anodal tDCS will enhance the induction of LTP (as measured by potentiation of AEP's) compared to Sham.**

## 2.0 Background

- 2.1 Significance of Research Question/Purpose: *Experience dependent plasticity is generally defined as the ability of a nervous system to dynamically shift functional or structural states in response to extrinsic and intrinsic factors. Research over the past 50 years demonstrates that experience dependent plasticity is a fundamental property of the brain and is critical for everyday functioning. It allows us to learn and recall patterns, predict and obtain reward, and guides response selection for adaptive behavior (Cooke and Bliss, 2006; Ganguly and Poo, 2013). Given its fundamental role in brain dynamics, maladaptive experience dependent plasticity can lead to debilitating conditions. Disrupted synaptic plasticity is thought to play a significant role in the pathophysiology of several severe psychiatric disorders, including schizophrenia (SZ), bipolar disorder and major depressive disorder (Elvsåshagen et al., 2012; Normann et al., 2007; Stephan et al., 2006). The contribution of disrupted plasticity is most clearly*

PROTOCOL TITLE:

VERSION DATE:

*implicated in SZ, a serious neuropsychiatric illness that impacts 1% of the population and presents with a host of positive, negative and cognitive symptoms. Therefore, treatments that can assess or even enhance plasticity have the potential to be of great clinical value.*

*Non-invasive neuromodulation via transcranial direct current stimulation (tDCS) is a promising method for modulating plasticity. Due to its low cost, tolerability and simplicity, the use of tDCS in both research and clinical settings has grown substantially. The beneficial effects of tDCS have been reported on a wide range of faculties, including learning and various cognitive abilities (Hill et al., 2016). Clinically, it has been used to treat a plethora of symptoms, from cognitive deficits to psychotic symptoms (Kekic et al., 2016). Despite the positive effects however, significant issues, such as moderate effect sizes and a high degree of variability in outcomes, limit the clinical potential of tDCS. One factor that contributes to these issues is the paucity of research that has investigated the mechanism of action of tDCS in humans. The vast majority of studies looking at this question have been conducted in animal or tissue models. Findings from these studies clearly demonstrate that tDCS effects are mediated by modulating plasticity mechanisms. However, due to the invasive techniques used to gather this data, recapitulating these findings in human subjects has not been possible. Techniques that can parallel the experimental procedures used in animal models are necessary to bridge the translational gap. A recently developed paradigm, termed stimulus specific plasticity (SSP), is a close parallel to the high frequency electrical stimulation protocols used in studies that investigated the impacts of tDCS on plasticity in animals and tissue slices. SSP utilizes sensory stimuli to evoke neural responses that can be recorded via the electroencephalogram (EEG), and has been shown to be functionally equivalent to the plasticity inducing paradigms used in model systems. This project has a strong translational application due to the paradigms that will be utilized. We will be translating much of the work that has been conducted in animal and tissue models which shows the modulatory effect of tDCS on synaptic plasticity. Translation of these findings to humans is necessary to better understand the mechanisms of tDCS and also to validate the animal models themselves. In addition, tracking tDCS effects with SSP allows the probing of neural plasticity in the sensory cortices, something that has generally been limited to the motor cortex in the past (via Transcranial Magnetic Stimulation). Given the fact that sensory processing is disrupted in psychiatric illnesses such as SZ, monitoring plasticity in these regions may also have a strong clinical significance. Finally, SSP allows the non-invasive assessment of the efficacy of treatments that are aimed at enhancing brain plasticity. In that sense, this project will serve as a proof of concept for studies that seek to assess effectiveness of tDCS intervention.*

PROTOCOL TITLE:

VERSION DATE:

*TDCS Modulates Synaptic Plasticity: tDCS is a neuromodulatory technique in which low-intensity direct current is conducted to the brain through scalp electrodes. Most commonly, two electrodes are utilized, an anode and a cathode. Anodal stimulation produces a shift in excitability that depolarizes neurons, while cathodal stimulation has opposite effects. These assumptions are only generalizations however, as it has been demonstrated that neuronal activity and morphology play a greater role in directionality of effects than previously thought (Kronberg et al., 2016). Though current spread from tDCS is rather diffuse, a degree of focality can be achieved as current density is highest directly underneath the electrodes (Bikson et al., 2012; Datta et al., 2009). Though the cellular mechanisms of tDCS are still under investigation, it is known that stimulation changes resting membrane potential (in a polarity specific manner), and modulates synaptic plasticity mechanisms of long term potentiation and depression (LTP/D). LTP refers to the lasting functional (or structural) enhancement of synaptic connections that occurs through coincident pre and postsynaptic activity. This concept, first postulated by Donald Hebb (Hebb, 1949), has several properties that make it an attractive candidate for serving as the substrate for learning and memory (Rioult-Pedotti et al., 2000). First, LTP is persistent, lasting from several minutes to months (Abraham et al., 2002). Second, it is input specific, in that the potentiation is restricted to active synapses only. Third, it is associative and cooperative, meaning that weakly stimulated synapses can still be potentiated if associated in time with other inputs that depolarize the postsynaptic cell (Kitajima and Hara, 1991). Lastly, LTP relies on the coincidence detecting mechanism provided by the NMDAR and is thus dependent on NMDAR activation (Rioult-Pedotti et al., 2000). Investigations of the effects of direct current stimulation on LTP/D have primarily been carried out in excised tissue samples from the hippocampus or the motor cortex of mice (Fritsch et al., 2010; Kronberg et al., 2016). In these studies, LTP is induced by applying a high frequency train of electrical impulses (HFS) to an afferent pathway. This causes the coincident activation of pre and postsynaptic cells, leading to enhancement of synaptic strength as measured by the slope of excitatory postsynaptic potentials (EPSPs). Multiple studies have shown that when applied during this protocol, direct current stimulation acts to modulate the potentiation of EPSPs. Anodal stimulation was found to enhance potentiation (Fritsch et al., 2010; Kronberg et al., 2016; Ranieri et al., 2012), while cathodal stimulation had varying effects depending on location of the recording electrode (Kronberg et al., 2016). It is important to note that direct current stimulation provides only a subthreshold change in membrane potential and does not on its own induce LTP. Thus tDCS relies on concurrent synaptic activity to enhance plasticity (Fritsch et al., 2010). The facilitation of LTP via tDCS has also been demonstrated *in vivo* in animal models. Here, learning of a motor task was*

PROTOCOL TITLE:

VERSION DATE:

*used to induce LTP in behaving mice who were treated with anodal or sham (placebo) stimulation over the motor cortex (Fritsch et al., 2010).*

*Immediately after learning the task, LTP was assayed by eliciting EPSPs from the layers II/III of the motor cortex. Mice who had received tDCS while learning the task displayed enhanced elevation of EPSPs compared to sham stimulated mice. In addition, the rate of learning on the motor task was significantly higher in the active stimulation group. These works demonstrate that tDCS effects on the brain are emergent from a modulation of plasticity mechanisms.*

*Very little work has been done that translates the findings from the aforementioned studies to human subjects. The only studies that have probed the effects of tDCS on plasticity in humans have done so in the motor cortex. These studies use Transcranial Magnetic Stimulation (TMS) triggered motor evoked potentials (MEP) as measures of synaptic potentiation. This method of probing plasticity is lacking in several regards. First, MEP's are not a direct measure of brain activity. Second, due to reliance on MEP's, these investigations are confined to the motor cortex, restricting the scope and the applicability of findings. Finally, the paradigm does not induce LTP and is not a close parallel to the HFS protocols used in animal/tissue models, thus limiting translational relevance.*

*SSP is a Non-Invasive Measure of Synaptic Plasticity: Recently developed techniques utilizing the EEG now enable the non-invasive interrogation of synaptic plasticity in the human cortex. As demonstrated first by Clapp et al., (2005), and since then by others (Teyler et al., 2005; Zaehle et al., 2007), it is possible to induce LTP in the human sensory cortices by the rapid presentation of sensory stimuli. It has been shown that a rapidly presented checkerboard pattern (a photic tetanus) can induce long lasting changes in evoked potentials (Teyler et al., 2005), spectral features (Clapp et al., 2006a), and hemodynamic response (Clapp et al., 2005a) in the visual cortex. Similar findings have been reported in the auditory cortex with rapid presentation of auditory tones (Clapp et al., 2005b). Here, the N100 component of the auditory evoked potential (AEP) was potentiated post auditory tetanus. The N100 component is a negative peak that emerges just anterior of the Cz electrode and is thought to emanate from the bilateral superior temporal gyri (Ford et al., 2016; Zaehle et al., 2007). The potentiation of the AEP post tetanus was independent of arousal state and persisted for over an hour without decrease. Studies of SSP in rats demonstrate that the potentiation effect is long lasting, NMDAR dependent and input specific, supporting the theory that SSP is indeed inducing LTP (Clapp et al., 2006b). This paradigm is thus a close parallel to the high frequency electrical stimulation that is used to induce LTP in animal and tissue models. These properties make SSP an ideal translational tool for*

PROTOCOL TITLE:

VERSION DATE:

*recapitulating the work done in models regarding the effects of tDCS on neural plasticity. To date no one has used SSP to analyze tDCS effects.*

*The fact that SSP allows the interrogation of plasticity in the sensory cortices is relevant from a clinical perspective as well. Several psychiatric disorders present with disrupted functioning of the sensory areas. This is especially notable in SZ, where disruptions of synaptic plasticity in the auditory cortex result in deficits of auditory perception and can lead to hallucinations (Gaebler et al., 2015; Sweet et al., 2009). A pertinent study by Mears and Spencer (2012) utilized the auditory SSP paradigm to assay LTP induction in SZ patients, finding a lack of potentiation in the N100 component (compared to healthy controls). A more recent paper utilized visual SSP to evaluate the effectiveness of D-cycloserine (an agonist of the NMDAR) on enhancing plasticity (Forsyth et al., 2015). Together these studies demonstrate that SSP can be used to both assay the integrity of the brain to support LTP, and as a tool to gauge the efficacy of treatments that are aimed at enhancing plasticity. Demonstrating the effects of tDCS on plasticity measures in healthy humans, is a necessary step prior to carrying this study out in a clinical population.*

- 2.2 Preliminary Data: N/A
- 2.3 Existing Literature: See Section 2.1

### **3.0 Study Endpoints/Events/Outcomes**

- 3.1 Primary Endpoint/Event/Outcome: *Change in amplitude of AEP as recorded by the EEG. Change in AEP is a proxy for brain plasticity.*
- 3.2 Secondary Endpoint(s)/Event(s)/Outcome(s): N/A

### **4.0 Study Intervention(s)/Investigational Agent(s)**

- 4.1 Description: *Transcranial Direct Current Stimulation (tDCS) is a noninvasive method of neuromodulation which applies low levels of electrical current to the scalp. TDCS can modulate plasticity and has been used for a variety of clinical and research purposes. We will apply tDCS bilaterally to the auditory cortex.*
- 4.2 Drug/Device Handling: *We will be using the StarStim8 (Neuroelectrics) device for tDCS and EEG recording. This device has been approved for use in research without an investigational device exemption due to meeting criteria for non- significant risk (NSR). In addition, the device has built in safety mechanisms which allow for the immediate cessation of stimulation should the subject become uncomfortable or if the impedance of the stimulation electrodes is too high. Stimulating electrodes will be placed over the auditory cortex and return electrodes will be placed over the supraorbital bone. 1 mA of current will be delivered for the duration of*

PROTOCOL TITLE:

VERSION DATE:

*stimulation. The device will be stored in a locked cabinet in our lab space. Our lab space on the 5th floor of the secure [name]. Only trained team members who are on the IRB protocol will have access to the locked cabinet.*

4.3 Biosafety: N/A

4.4 Stem Cells: N/A

## 5.0 Procedures Involved

5.1 Study Design: *The study will be conducted in a blinded, within-groups design involving two separate study sessions. The two sessions will consist of simultaneous tDCS and EEG recording. Each participant will receive both active and sham tDCS over the course of the two sessions (but not within a single session). Order of stimulation type will be counterbalanced across participants. The two sessions will be spaced at least 24 hours apart. The consent process will be done at the first study session. The primary outcome measure will be the difference in the amplitude of the ERP's (specifically the N100 component) recorded before and after tDCS. This difference is reflective of the capacity of the sensory cortex to support synaptic plasticity.*

5.2 Study Procedures:

- Screening Visit: *The screening process will happen over email or phone (depending on how participant makes contact). Potential participants will be provided with information about the study using an established script and will be asked a series of questions to determine if they meet basic inclusion/exclusion criteria (see below). They will be told about the basic aims of the study, and those interested in participating will be scheduled for the study.*
- Study visits: *Visits will take place at our [name] offices, the Ambulatory Research Center (ARC) at the department of Psychiatry, or at the clinical spaces at our St. Louis Park location. At the first study session, the participants will complete the informed consent process. The participant will also be told that this is not a treatment study and no benefits to the participant are expected from the study. After, and if, they complete the process, the participant will fill out the tDCS Side Effect Questionnaire (TSEQ), and the Edinburgh Handedness Inventory. These two brief questionnaires ask about potential side-effects of tDCS and the subject's handedness respectively. After the paperwork has been completed, the participant will undergo EEG and either active or sham tDCS (see embedded figure). The stimulation and the recording will be provided using the StarStim Neurostimulator (Neuroelectrics, Inc.). This device has been approved for use in research in the United*

PROTOCOL TITLE:

VERSION DATE:

*States without an investigational device exemption due to meeting criteria for non-significant risk. The device utilizes standard Ag/Cl electrodes embedded in an easy to use neoprene cap. A small amount of conductive gel is applied to each electrode before insertion into the head cap. Electrodes will be positioned on the subject's scalp according to the international 10/20 electrode placement system. During EEG recording, all electrodes will be utilized to record brain signal. The session will begin with EEG recording while the participant engages in a visual search task. Immediately after, either a passive Auditory Oddball paradigm or a passive Visual Oddball paradigm (these tasks are described in detail in the instruments section) will begin. They will be seated in front of a monitor as they observe visual stimuli or will be wearing insert headphones through which auditory stimuli will be delivered. After the first Oddball task, simultaneous EEG and tDCS will commence for a period of 10 min. During simultaneous EEG and tDCS, two electrodes will be used to deliver stimulation, while the remaining electrodes continue to record EEG. The two stimulation electrodes will be positioned bilaterally over the auditory cortex (T3/T4). In the anodal group the device will deliver 1mA of current through each stimulating electrode. The current is initiated in a ramp like fashion over a 10 sec period from 0mA to 1mA. Once at 1mA, the current is held constant for the duration of the session. Should the participant not be able to tolerate a current of 1mA due to pain or irritation, the current will be decreased down to a minimum of 0.5mA. If 0.5 mA is still not tolerable, the participant will be removed from the study. The sham procedure involves only 40 sec stimulation at 1mA and then drops to 0mA with 15ms pulses every 550ms. This simulates the tingling sensations that are often associated with active stimulation. 15min into the stimulation session the sensory tetanus will commence. The auditory tetanus involves the presentation of a 1000Hz tone at a rate of 13Hz for a period of approximately 5min. The visual tetanus involves the presentation of the visual stimulus (either a horizontal or vertical grating) at a rate of 9Hz. Sensory tetanus and tDCS will end at the same time. Briefly after tetanus and tDCS, the participants will perform the second oddball task as well as a final visual search task. 30 min after the cessation of tDCS, a final oddball task will be conducted. After the completion of the EEG recording, the head cap will be removed and the participant will be given the opportunity to wash their hair (towels and shampoo provided). The two study sessions will be identical, differing only in type of tDCS applied (sham or active).*

- Precautions Taken: *tDCS is considered to be a safe brain stimulation technique that rarely result in adverse events. There is currently no evidence of serious side-effects. We will discontinue any participant who experiences sores at the tDCS administration site, headaches that*

PROTOCOL TITLE:

VERSION DATE:

*impair global functioning, and worsening psychosis. Mild side-effects typically resolve upon discontinuation tDCS. The participant may choose to discontinue stimulation at any time during the session if experiencing discomfort or side effects. No other risks are anticipated. Nonetheless, in order to minimize risks, study staff will be using standards of administration that have been shown to be safe in numerous other studies and across more than 2000 studies (Liebetanz et al., 2009; Nitsche et al., 2007; Poreisz, Boros, Antal, & Paulus, 2007) using tDCS; this includes length of administration, magnitude of the current, size of electrode sponges used, and method of applying stimulation. Any unanticipated problems or adverse events will be reported according the University of Minnesota IRB standard operating procedure. 2. Participants will be informed that they are not required to answer any questions or participate in any activities which make them uncomfortable. 3. The results of this study may be published or presented but the participant's identity and records will not be revealed unless required by Federal Law. A Federal Law allows the U.S. Food and Drug Administration, Office for Human Research Protections, Government Accountability Office and other Federal agencies, the Research and Development Committee, representatives of USAMRMC, Henry M. Jackson Foundation, the University of Health & Biological/Medical Application Form 11 Minnesota Institutional Review Board (IRB), and/or the Institutional Review Board (IRB)/Human Studies Subcommittee of the VA Medical Center to review records. Because of the need for these inspections, absolute confidentiality cannot be guaranteed. However, every effort would be made to minimize these risks by providing the participant with a unique numerical identifier at the beginning of the study in order to protect their actual identification and maintain complete confidentiality.*

5.3 Study Duration: *We plan on enrolling participants through May 2019. Data analysis should be completed by December 2019.*

5.4 Individually Identifiable Health Information: *Basic information regarding participants, name, email, phone number, address and DOB will be collected. See the HIPCO form for more details.*

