8.2 Exclusion Criteria: *Exclusion criteria are listed below:*

- *History or tDCS or other cortical energy exposure within past 12 months*
- *History of seizures or epilepsy*
- *Cranial metallic plates/screws*
- *Implanted devices*
- *History of craniotomy*
- *History of eczema on scalp*
- *Bipolar disorder or Depression diagnosis*
- *Cornrows or dreadlocked hair*
- *Impaired hearing*

8.3 Screening: *The screening process will happen over email or phone (depending on how participant makes contact). Potential participants will*

PROTOCOL TITLE:

VERSION DATE:

*be provided with information about the study using an established script and will be asked a series Health & Biological/Medical Application Form 7 of questions to determine if they meet basic inclusion/exclusion criteria.*

*They will be told about the basic aims of the study, and those interested in participating will be scheduled for the study. At the study visit, the participants will first complete the informed consent process*

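### The active and sham sessions may be only 24 hours apart, and nothing in the protocol shows that the induced plasticity has gone by then, so unequal carry-over could bias the comparison in either direction

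*Combined protocol and SAP*

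**What the plan says.** The trial is a two-session crossover in healthy volunteers (protocol, section 5.1). On spacing it says only "The two sessions will be spaced at least 24 hours apart", with no upper limit and no reason for the figure. On order: "Order of stimulation type will be counterbalanced across participants". The primary outcome is the N100 amplitude change from before to after tDCS, so each session has its own baseline.

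Section 5.2 states that the two sessions differ only in whether stimulation is active or sham. For the auditory version, "The auditory tetanus involves the presentation of a 1000Hz tone at a rate of 13Hz for a period of approximately 5min". Section 5.2 also describes a visual oddball and a visual tetanus, so the repeated 1000 Hz tone concerns participants on the auditory task, which is the task of Aim 1.

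On persistence, section 2.1 says of LTP in general that "LTP is persistent, lasting from several minutes to months". Of the human auditory evoked potential after tetanus it says that the increase "persisted for over an hour without decrease", and it presents the paradigm as inducing LTP. No end point is given.

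Section 8.2 excludes anyone with "History or tDCS or other cortical energy exposure within past 12 months". Section 15.3 plans a two-way ANOVA with a multiplicity correction and names no order, period or carry-over term.

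**The concern.** A crossover estimate is unbiased only if what remains of session 1 affects the session 2 measurement equally whichever condition came first. Here the intervention is meant to change plasticity, the tetanus is meant to induce a lasting change, and the hypothesis in section 1.0 is that active stimulation induces more of it than sham. If any of that change survives to session 2, the natural expectation is that more survives after active.

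Two mechanisms would carry this into the outcome. Under occlusion, residual potentiation raises the session 2 baseline and leaves less room to potentiate, so the session 2 change is smaller. Under priming, earlier potentiation makes the session 2 change larger. The first overstates the active-versus-sham difference and the second dilutes it. At stake is the only endpoint in the protocol, and the damage cannot be fully repaired once the data are collected.

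**Working it through.** **Inputs from the protocol.** Minimum gap 24 hours, counterbalanced order, within-session change as outcome (5.1); 35 completers (10.1, 15.2); power 0.80 for effects above 0.450 and a cited effect above 0.68 (15.2). The protocol gives no figure for carry-over, so every carry-over size below is an assumption.

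**The plan's own figure.** Section 15.2 states neither alpha nor sidedness. A paired t-test with n = 35, standardised effect 0.450 and alpha 0.05 has power 0.734 two-sided or 0.832 one-sided; neither is 0.80. That is a separate matter and the carry-over point does not depend on it. I use the two-sided 0.734 as the reference.

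**Bias formula.** Let A and S be the true mean changes under active and sham, and let c_A and c_S be what a previous active or sham session adds to the session 2 change.

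- Active first: A − (S + c_A)
- Sham first: (A + c_S) − S
- Mean of the two orders: (A − S) − (c_A − c_S)/2

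Equal carry-over (c_A = c_S) cancels. A residual that moves the pre and post recordings by the same amount makes both terms zero. A period effect π common to both orders enters as −π and +π and also cancels. What is left is half the differential carry-over. A period term in the model estimates this same mean of the two orders, so it does not remove the bias.

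**Size under an assumed differential.** Take a true standardised difference of 0.45, n = 35, two-sided 0.05, and hold the SD of the paired difference fixed.

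| Differential, as share of true effect | Direction | Shift | Expected effect | Power |
|---|---|---|---|---|
| 0 | none | 0 | 0.450 | 0.734 |
| 25% | priming | −12.5% | 0.45 × 0.875 = 0.394 | 0.619 |
| 50% | priming | −25% | 0.45 × 0.75 = 0.338 | 0.492 |
| 25% | occlusion | +12.5% | 0.45 × 1.125 = 0.506 | overstated |
| 50% | occlusion | +25% | 0.45 × 1.25 = 0.563 | overstated |

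**One mechanism spelled out.** Suppose a fraction f of the session 1 change persists and reduces the session 2 change one for one, so c_A = −fA and c_S = −fS. The estimate is then (A − S)(1 + f/2). For illustration take S = 0.68 and A = 0.68 + 0.45 = 1.13, with f = 0.5:

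- Active first: 1.13 − (0.68 − 0.565) = 1.015
- Sham first: (1.13 − 0.34) − 0.68 = 0.11
- Mean: 0.5625 against a true 0.45, which is +25%

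The 0.68 and 0.45 need not share a standardiser, but the percentage bias depends only on f. In this model A = S gives no bias.

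**How fast would the effect have to fade?** With exponential decay the residual at 24 hours is 0.5^(24/half-life in hours). Assumed half-lives of 2, 12, 24 and 72 hours leave 0.02%, 25%, 50% and 79%. So 24 hours is ample if the effect halves within a couple of hours, and not if it halves in half a day or more. The protocol reports no decrease over somewhat more than an hour and nothing later, so it cannot separate these cases.

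**The case against.** The strongest reply is that the design already has two safeguards. Order is counterbalanced, and each session is measured against its own baseline. Together they remove equal carry-over and any residual that simply lifts the whole session 2 recording. Bias therefore needs occlusion or priming, and no section documents either. This stands: a raised session 2 baseline alone would not bias the result.

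Three stronger readings are tempting, and the documents do not support them.

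- *That the protocol says the auditory effect lasts for months.* That range is given for LTP in general, with a reference whose title concerns the hippocampus. For the human auditory response the protocol reports only that it outlasted an hour.
- *That the 12-month exclusion shows 24 hours to be too short.* It is an entry criterion with no stated purpose and could serve naivety, blinding or safety. The contrast is a reason to ask for a justification, not proof of inadequate washout.
- *That carry-over would create a false positive.* In the occlusion model a true null stays unbiased. Bias under the null would need a lasting effect of tDCS itself on the session 2 change, and section 2.1 says that direct current alone does not induce LTP.

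It is also fair that 24 hours is only a minimum, so actual gaps may be longer. Nothing requires that, however.

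**Conclusion.** The interval is not justified by the protocol's own account of the effect it sets out to induce, and carry-over that differs between the two orders is uncontrolled. That much rests on the text. The bias formula, half the differential carry-over, is exact for the mean of the two orders. The percentages are conditional: 12.5% to 25% either way follows from an assumed differential of 25% to 50% of the true effect, and the true figure may be nil. A reader might infer that the result will be inflated, or that it will be diluted; the documents determine neither direction nor size. The point is a worthwhile and inexpensive improvement to the design, not a demonstration that the trial will give a wrong answer.

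**What to change.** 1. In section 5.1, lengthen the minimum interval between the two measurement sessions well beyond 24 hours. The sponsor should choose the length and justify it against the persistence statements in section 2.1 and the exposure criterion in section 8.2. The documents give no basis for a particular number of days.
2. In section 15.3, include order and period in the analysis. This deals with period effects and with the unavoidable 18/17 split of 35 completers; it does not remove differential carry-over.
3. Prespecify a comparison of the session 2 with the session 1 pre-tDCS N100, by order. The recordings are already planned. Priming that leaves the baseline unchanged would escape this check, so a clean result is not proof of no carry-over.
4. Report the first-session-only active-versus-sham comparison as a sensitivity result in all cases, not only when the baseline check is positive, so that reporting does not depend on a pre-test. State its low power. For a paired effect of 0.45 the between-group effect is 0.45 × √(2(1 − ρ)), with ρ the between-session correlation of the changes. With 18 versus 17 and two-sided 0.05, power is 0.25 at an assumed ρ of 0.5, ranging from 0.45 at ρ = 0 to 0.13 at ρ = 0.8.

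The cost is protocol wording and scheduling, with no added visits or procedures. The downside is slightly more loss between visits and a longer calendar within the May 2019 enrolment limit. The 80 consents allowed for 35 completers give some room, though they must also absorb withdrawals for poor EEG quality (section 12.1), and no attrition rate is stated.
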